**Additional procedures the SME instructor will complete during the week before Orientation:**

- Before 8 AM on the day of the Orientation, the SME instructor will send (via Secure File Transfer - SFT) the list of randomized MBSR subjects with their contact information (Name, Email Address, Phone Number) to the MBSR instructors.

**Other study procedures the SME instructor will complete:**

Once an SME instructor randomizes a subject to MBSR or SME, that SME instructor will be responsible for following that subject throughout the time that the subject is in the study, and completing any study procedures that cannot be completed by the blinded research coordinators, including:

- By Class #1, record the number of subjects in their cohort randomized to each group (and any other needed information) in the Unblinded Classes sheet in the Excel Study Tracking Spreadsheet in Google Drive. This information will be used by unblinded research team members e.g. the SME instructors, to check that the correct number of subjects started up the MBSR and SME Daily Diary surveys after Class #1. Blinded study team members cannot be aware of the number randomized to each group in a cohort since this could reveal group assignments.
- Coordinate the documentation of attendance at the MBSR or SME sessions for each subject in their cohort (See the section below entitled “Attendance”)
- To encourage subject retention in the study, and to parallel what is commonly done in MBSR, after Class #8, the instructors will invite the subjects to participate in additional MBSR or SME Retreat sessions and monthly booster sessions (See SME Instructor Email Template After Class #8 MBSR Booster Reminder and SME Instructor Email Template After Class #8 SME Booster Reminder). The monthly booster sessions in months 3 to 6 are required sessions for the study. The remaining booster sessions, and any additional Retreat sessions after Class #8, are optional. Attendance will be recorded at these additional sessions, however subjects will not receive any financial compensation for participating in the optional sessions.
- The SME instructor will serve as the point-of-contact for any and all communications between the MBSR/SME instructors and the blinded research team about subjects in a manner that does not reveal a subject’s group assignment (See the section below entitled “Blinding”).
- A subject’s SME instructor will be the one main point person that the subject can contact with any questions about the study. This will be very important in building rapport with the subject and encouraging retention in the study.
- Any other study procedures that cannot be completed by the blinded research coordinators.

**Attendance:**

The SME instructor for each cohort/wave will coordinate the documentation of attendance for each MBSR and SME subject in their cohorts throughout the 6 months that the subjects are in the study. Subjects’ attendance will be documented for the Orientation session, Class #1 to 8, the Retreat session, Booster sessions #1 to 4, and

any additional optional study booster sessions and retreat sessions that subjects participate in while they are in the study. Attendance will be recorded by the MBSR or SME instructor at the beginning of each Zoom session. For the purposes of this study, 'attendance' is defined as attending the class in full, entering the class late, and/or leaving the class early (e.g. partial attendance will count as full attendance).

**Within 24 hours of each session**, the SME instructors will record the attendance for each of the MBSR and SME subjects, in the Blinded Attendance Log in REDCap. Blinded study team members will be able to review the Blinded Attendance Log as it will not contain any information that would reveal group assignments.

Procedures for when a subject misses a session: The protocol for contacting subjects who miss a session will be similar for both MBSR and SME groups. The following procedures will be completed when a subject misses an MBSR or SME session that they are assigned to:

- If a subject misses the Orientation session after being randomized, the subject's instructor (either MBSR or SME) will contact the subject and offer them an individual Orientation session. If a subject does not complete Orientation after being randomized to MBSR or SME prior to Class #2, the SME instructor will notify the research coordinator and the subject will be withdrawn from the study.
- If a participant misses a Class #1 to 8 session, Retreat session or booster session, the subject's instructor (either MBSR or SME) will complete the following procedures:
  - Send a follow-up email if someone misses a class and let them know we missed them.
  - Encourage them to continue to follow along with the home practice and do their best to attend all the remaining sessions that they are assigned to.
  - Offer to be available by email, phone call, or schedule a time to meet usually before or after the next class, if they wish to have a private discussion.
  - The SME instructor will ask the MBSR instructor to let them know if they receive any communication from a study participant regarding a missed session.
- After 48 hours of the missed session, if a study participant in MBSR or SME, has not communicated with the instructors regarding a missed session, the SME instructor will call the participant.
- Each MBSR and SME instructor will keep a Participant Contact Log, where they record each time they attempt to contact a study participant in MBSR or SME (via phone or email) for missing a session. Each instructor will maintain their Participant Contact Log securely themselves, and they will hand this log in to the research team at the end of the study. If the research team needs any information on this log before then, the MBSR instructor will securely share their log with the SME instructor who will securely share the needed information with the research team in a blinded manner. This log will include the following for each contact attempt:
  - Date and time of each contact attempt
  - Whether the contact attempt was via phone or email
  - Whether or not the subject responded (confirming successful contact), and if the subject responded:
    - ❖ Date of subject response
    - ❖ Whether the subject's response was via phone or email
    - ❖ Any reasons the subject provided for missing the session, and
    - ❖ Whether the subject confirmed that they will or will not be attending the subsequent sessions.
- If a subject has 2 consecutive unexcused absences from MBSR or SME, the SME instructor or other unblinded research coordinator will contact the subject, and encourage the subject to continue to follow along with the home practice and do their best to attend the sessions. Subjects will be advised to contact their instructor if they have any questions or concerns about their sessions or home practice.

**Blinding:**

The PI, research coordinators and all other research team members involved in the collection or review of outcomes data will be blinded. The random assignment of subjects to MBSR or SME will not be communicated to any research team member who will be collecting or reviewing outcomes data. The subjects, SME instructors, MBSR instructors, data manager, video coders, [name] will be asked to keep the study group assignments concealed from the blinded investigators and study personnel.

The SME instructors, MBSR instructors, and other unblinded research team members will be asked not to reveal the number of study subjects in an MBSR course, or in an SME course, to the research coordinators and other blinded research team members.

The research coordinators and other blinded research team members will be:

- Blinded to the number of subjects randomized to MBSR in a cohort/wave
- Blinded to the number of subjects randomized to SME in a cohort/wave

The research coordinators and other blinded research team members will be:

- Aware of the total number of subjects randomized in a cohort/wave

Subjects will be asked to keep their study group assignment concealed from the blinded study personnel, including the research coordinators and other study personnel that they meet during the study visits. At the beginning of any phone call, study visit, or other contact with a subject, blinded research team members will remind subjects not to say anything that would reveal their group assignment e.g. instructors' names, specifics about their classes or Daily Diary survey questions, the PSU Zoom link for their classes, etc.

The research coordinators and other blinded research team members will not have access to the Experience Sampling Surveys in REDCap, which will be managed by unblinded research team members e.g. the SME instructors. Additionally, the PSU Zoom links for the classes will only be available to [name] and the instructors as these individuals will not be blinded.

Procedures in the MBSR group will parallel procedures in the SME group to maintain blinding. As an example, since subjects in the MBSR group are not allowed to continue with MBSR if they miss Orientation, the same will apply for subjects in the SME group. Additionally, if a session for one group needs to be canceled for any reason, the concurrent session for the other group will also be canceled.

The SME instructors will serve as the point-of-contact for any and all communications between the MBSR/SME instructors and the blinded research team about subjects, in a manner that does not reveal a subject's group assignment. The MBSR instructors and SME instructors will be given each other's contact information. Any subject-specific information, including any potential adverse events that an instructor becomes aware of in an MBSR subject, or in an SME subject, (e.g. requiring a change in MBSR or SME practice recommendations), will be communicated to the blinded research coordinator through the SME instructors, in a manner that does not reveal the subject's group assignment. The MBSR instructors will avoid directly communicating with the blinded research coordinator and other blinded research team members about specific subjects. The MBSR instructors will directly communicate information about MBSR subjects to the SME instructors. The SME instructors will communicate information about MBSR subjects and SME subjects to the blinded research coordinator in a manner that does not reveal which

instructor the subject reported the adverse event to or any other information that would reveal the subject's group assignment. To accomplish this, we will minimize the 'discussion' aspect of how the SME instructors report potential adverse events or any other information about a subject to the research coordinator because discussion of the report may lead to unblinding/may make it obvious as to which instructor it was reported to if the SME instructor doesn't know much about the encounter. The SME instructors will simply state e.g. "Participant ID 123 has reported  to an instructor." The research coordinator will then follow up with the subject via phone for formal adverse event documentation. If indicated, the research coordinator will complete an Adverse Event form. Similarly, any subject-specific information that the research coordinators need to communicate to the instructors will go through the SME instructors, and then the SME instructors will pass the information along to the MBSR instructors if the subject is in the MBSR group.

Blinded research team members will not participate in any of the study MBSR or SME sessions.

**Subject Expectancy:** To minimize the influence of subjects' expectations, subjects will be informed that the study is designed to test the effects of two different types of stress reduction programs, one of which is combined with health education. Subjects will be informed that they will be asked to participate in one or more of the following activities during the study sessions: breathing exercises, meditation, stretching exercises or health education activities. Further, subject expectancy will be assessed at the baseline, 2-month, and 6-month, study visits using a Stress Reduction Expectancy Scale (SRES) modified from the Acupuncture Expectancy Scale.

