Who will be managing and aggregating this data: The research coordinators will initialize the devices, and upload the (optional) collected Actigraph data into the ActiLife software platform. Biometric data (height, weight, date of birth, dominant side, etc.) is entered at the time the devices are initialized and prepared for distribution for data capture. The most current updated weight measurement available to the research coordinator will be used to initialize the device (whether that be measured at an in-person study visit, extracted from the medical records, or self-reported by the participant, when necessary). This information is important to obtain accurate metabolic equivalents (METs) calculations in the software algorithms/formulas (because a change of a few kilograms will have an effect on the energy expenditure and METs calculations). When applicable/necessary, it is possible that the biometric data may also be entered/updated at the time of scoring at the end of the study. The research coordinators will work with the data manager/statistician to reconcile any data entry or quality issues. *Refer to the Actigraph Device Data Monitoring SOP for more detailed information and procedures.* As the processing and wear-time validation of accelerometer data is a developing and evolving field, the wear-time validation algorithm and criteria will be decided for analysis at the end of the study, when more current literature can be reviewed. If possible, ideally the wear period will meet either the initial Sallis validation criteria of at least 5 valid days containing at least 10 valid hours per day, or the alternate Sallis validation criteria of at least 66 valid hours (Cain &

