Geremia, 2012). At the end of the study, once the wear-time validation algorithm and processing criteria are decided upon after review of more current literature at that time, the Actigraph data will then be processed and scored for analysis, likely using Freedson VM3 2011 for Energy Expenditure Scoring and Cut Points/MVPA Scoring (Sasaki et al., 2011), and Freedson 1998 for METs (unless Freedson VM3 2011 or updated algorithms become available options later at the time of scoring and analysis) (Freedson et al., 1998). Actigraph data will be reviewed regularly by the data manager/statistician. [name], MS, ACSM EP-C, an exercise physiologist experienced in using the Actigraph, will be briefly available for consultation with the research team regarding questions in the use of the Actigraph wGT3X-BT and the ActiLife software that will be used to score the data. The research team will read the ActiLife 6 User's Manual, the User Guide for the ActiGraph wGT3X-BT + ActiLife, and Sallis's Accelerometer Data Collection and Scoring Manual For Adult & Senior Studies (Cain & Geremia, 2012).

How often will this data be collected throughout the trial: This optional data will be collected for 7 days around each of 3 study visit time points (baseline, 2-month and 6-month).

What important pieces of data are being collected from the Actigraph wGT3X-BT devices throughout the trial:

The optional Actigraph will be worn for 7 days and data will be stored as 10 second epochs (and possibly later converted to 60-second epochs). This data will be used to determine average daily:

- Step count data
- Sedentary – Length of time in minutes in Sedentary activity [<100 counts per minute (60-s epoch)]
- Light - Length of time in minutes in Light physical activity [100-1951 counts per minute (60-s epoch)]
- Moderate - Length of time in minutes in Moderate physical activity [1952-5724 counts per minute (60-s epoch)]
- Vigorous - Length of time in minutes in Vigorous physical activity [5725-9498 counts per minute (60-s epoch)]
- Very Vigorous - Length of time in minutes in Very Vigorous physical activity [ $\geq$ 9499 counts per minute (60-s epoch)]

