### **Data Security**

Unblinded research team members e.g. the SME instructors will have access to the randomization list in REDCap so that they will be able to check and make sure that subjects are completing the correct Daily Diary Survey questions that correspond to their group assignment, MBSR or SME.

During the study, subjects will be compensated an additional \$15 if they respond to at least 70% of the Experience Sampling Surveys by their 2-month study visit.

Between the baseline study visit and Class #8, unblinded research team members e.g. the SME instructors will periodically review reports of subjects' Experience Sampling Survey response rates, and if a subject's response rate for the Experience Sampling Surveys (Stress and Cravings or Daily Diary) ever falls below 70% in a week, the SME instructor or other unblinded research coordinator will call the subject to troubleshoot.

Between the 2-month study visit and the 6-month study visit, the SME instructor or other unblinded research coordinator will be making monthly phone calls to the subjects to remind them of their booster sessions and encourage retention in the study. During these monthly phone calls, the research coordinator will encourage subjects to continue to respond to as many of the Experience Sampling Surveys as they are able to as their responses are very important in helping the research team better understand how day-to-day stresses affect people living with diabetes.

Who will be managing this data: Unblinded research team members e.g. the SME instructors will be managing this data. Due to the nature of this data, specifically because the MBSR and SME groups have different Daily Diary of home practice questions and responses, which would reveal group assignments, the research team members managing this data e.g. the SME instructors will not be blinded. Blinded study team members will not have access to the Experience Sampling Surveys in REDCap.

Who will be analyzing this data: The study biostatistician will analyze this data with input from [name]. However, any data that identifies the group assignments of the subjects (e.g. Daily Diary survey questions and responses about their home practice, instructors' names, etc.) cannot be analyzed by the study biostatistician or any of the blinded study team members until the study is unblinded.

**At the end of the baseline visit, if a subject is deemed fully eligible for inclusion into the study, the research coordinator will:**

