Randomization to MBSR or SME control will be performed within REDCap using a pseudo-random number generator via the PLAN procedure within SAS software, version 9.4 (SAS Institute Inc., Cary, NC). Personnel in the Department of Public Health Sciences will use the PLAN procedure within SAS software to generate a randomization list using variable-size, random permuted blocks to ensure that the number of subjects in each treatment arm is balanced after each set of B randomized subjects, where B is the block size. Using a 1:1 allocation ratio, there will be 145 subjects assigned to each study group. Randomization will be stratified by insulin vs. non-insulin treated subjects to make sure the two groups are balanced as this is a potential confounder. Personnel in the Department of Public Health Sciences will choose the block sizes without revealing it to any of the blinded investigators or study personnel who will be collecting and reviewing outcomes data. Study group data will be presented in a blinded fashion within DSMB reports.

Randomization to MBSR or SME control will be performed by the SME instructors in REDCap during the Randomization phone call as described below. Study group assignments will not be communicated to research personnel who will be collecting and reviewing outcomes data. The SME instructors will communicate the study group assignments to the subjects and the MBSR instructors. The subjects and instructors will be asked to keep the assignments concealed from the blinded investigators and study personnel. The PI, research coordinators and all study personnel involved in the collection and review of outcomes data will be blinded.

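### The rule that every outcome reviewer is blinded does not hold as written for the optional Actigraph outcome, because its reviewer is a data manager/statistician and the data manager is listed with those who hold assignments

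*Combined protocol and SAP*

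**What the plan says.** The blinding rule appears twice in section 7.2.4. The randomization text says "The PI, research coordinators and all study personnel involved in the collection and review of outcomes data will be blinded". The Blinding subsection repeats it and adds that the random assignment "will not be communicated to any research team member who will be collecting or reviewing outcomes data". Neither place makes an exception.

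The next sentence of the Blinding subsection names the people who are to keep assignments from the blinded investigators and personnel. The list begins "The subjects, SME instructors, MBSR instructors, data manager, video coders" and ends with a removed name.

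The accelerometer text in section 7.2.3 gives two tasks to a combined role. On quality control: "The research coordinators will work with the data manager/statistician to reconcile any data entry or quality issues". On review: "Actigraph data will be reviewed regularly by the data manager/statistician". The same text leaves the valid-wear algorithm, its criteria and the final scoring choices to the end of the study, after a look at the literature of that time.

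Under Data Security in section 7.2.3, data that identify a subject's group "cannot be analyzed by the study biostatistician or any of the blinded study team members until the study is unblinded". The biostatistician is thereby grouped with the blinded team.

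**The concern.** A trial that cannot blind its participants or instructors relies on blinding the people who collect, clean and score the outcomes. The protocol takes that seriously, and states the protection as a property of everyone who handles outcome data. If one role on the assignment-holding side also reviews an outcome during the trial, that property is not true as stated, and a report that repeats it would be inaccurate for that outcome.

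Actigraph processing is where this matters, because it involves judgment: which days count as valid, how many hours make a day, and which algorithm and cut-points are used. Those choices are open while the data are being reviewed. Knowing the arms while seeing the accumulating data, before the rules are set, is an avoidable route for bias, whether or not anyone acts on it.

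**Working it through.** There is no arithmetic here. The check sets five pieces of text side by side.

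1. **The rule.** Everyone who collects or reviews outcome data is blinded, and assignments are not passed to them (section 7.2.4, randomization text and Blinding). No exception is stated.
2. **Who holds assignments.** The data manager is named with the participants, both sets of instructors and the video coders as people who must conceal assignments (section 7.2.4, Blinding). Concealing something presupposes knowing it, and the sentence sets these people against the blinded personnel. No sentence says outright that the data manager is unblinded, so this is a strong inference rather than a quotation.
3. **Whether Actigraph data are an outcome.** Table 3 lists accelerometer data, marked optional, under behavioral outcomes at baseline, 2 months and 6 months. Section 1.3 does not name them but includes other behavioral measures among the secondary outcomes. Regular review of these data is therefore outcome review.
4. **Who reviews them.** The data manager/statistician does so regularly, and the same role resolves entry and quality issues with the research coordinators, who are blinded under item 1.
5. **Where the statistician stands.** The biostatistician is treated as blinded (section 7.2.3, Data Security). I take the statistician in the combined label to be this person or a colleague with the same status; the document does not say.

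The slash can be read in three ways:

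- *One person in both roles.* A person on the concealment list reviews an outcome, which breaks the rule. If that person is also the study biostatistician, the biostatistician's blind is affected too.
- *Two people, and both or either may review.* The data manager may review an outcome, so the rule is not assured.
- *Always the blinded statistician.* There is no conflict, but no sentence says this, and the words data manager would then be wrong in the accelerometer text.

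The text needs correcting on every reading, and the blinding statement fails or is not assured on the first two.

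On timing, the accelerometer text places the wear-time and scoring decisions at the end of the study and gives the state of the literature as the reason. It says neither who decides nor that the decision comes before unblinding. Regular review during the trial therefore precedes the choice of rules.

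**The case against.** The strongest reply is that this is a loose label on a minor measure. Actigraph wear is opt-in, the output is recorded by a device, the coordinators upload it, and the scoring is expected to use published algorithms and cut-points. The sentence on reconciling quality issues follows text about the weight and other biometrics entered to initialize the devices, so the joint work may be clerical. The Blinding paragraph is itself a control, since it asks the data manager to conceal assignments. The accelerometer text also points to a separate procedure for monitoring Actigraph data, which is not in the document and may settle who reviews what. All of this stands, and it limits the weight of the point. It does not remove the mismatch between an unqualified rule and the role named as reviewer.

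A reader might infer more than the document supports:

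- *That the data manager reviews outcomes in general, including HbA1c.* Nothing shows this. The Data and Safety Monitoring Plan (III.B) gives outlier and missing-data queries on primary and secondary outcomes to the biostatisticians.
- *That the data manager chooses the wear-time rules or which days count.* The document does not say who does. The risk is that nothing excludes it.
- *That the data manager sees the Daily Diary forms.* The protocol gives their management to unblinded team members, with the SME instructors as its example, and does not name the data manager.
- *That contact between the data manager and the coordinators is uncontrolled.* The instruction to conceal applies to it. The scripted channel in section 7.2.4 was written for instructors' reports about participants, so its silence on the data manager is not a gap in that procedure.
- *That per-arm class counts leak.* Section 7.2.4 has them recorded "in the Unblinded Classes sheet in the Excel Study Tracking Spreadsheet in Google Drive" and says that blinded staff must not know them. File permissions are not stated, no text says blinded staff can open the sheet, and counts alone do not identify anyone's arm.

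**Conclusion.** The point holds in a limited form. As written, the statement that all outcome reviewers are blinded is not true, or not assured, for the accelerometer outcome at its three time points, because the reviewing role includes one listed among those who must conceal assignments. The conclusion rests on two assumptions: that being asked to conceal assignments means holding them, and that the combined label does not always mean the blinded statistician alone. If the second fails, only a wording error remains.

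No effect on the primary HbA1c analysis, on power or on type I error follows from the text. The size of any bias in the Actigraph results cannot be estimated from the document. The point is still worth acting on, because the processing rules for this outcome are left open without a requirement that they be fixed while the decision-makers are blinded.

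**What to change.** 1. In the accelerometer text of section 7.2.3, replace the combined data manager/statistician label, in both places, with the blinded biostatistician. If one person fills both roles, or if the sponsor prefers, instead withdraw the data manager's access to assignments and delete the role from the concealment list in section 7.2.4. The document names no task for the data manager that requires the assignments.
2. State that blinded staff will decide and document the Actigraph wear-time and scoring rules before the study is unblinded. The literature review can still take place at the end of the study.
3. As housekeeping, state that the sheet holding per-arm class counts is open to unblinded roles only.

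The cost is a few sentences in sections 7.2.3 and 7.2.4 and a check of REDCap and file permissions. Sample size, visits, measurements and the analysis model do not change. No new staff are needed if the data manager and the biostatistician are already two people; if they are one, the alternative in item 1 avoids an appointment.
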